7.2.1. B-scan Ultrasound

B-scan ultrasounds will be used to assess total PVD. The images will be submitted to and evaluated by the B-scan expert reader.

B-scan ultrasounds will be taken for all subjects:

- At Visit 1 (screening visit) for **potential study eye(s)**
If 1 of the subject's eyes is excluded based on an eligibility criterion that does not need confirmation by the B-scan expert reader or the CRC, no B-scan ultrasound needs to be performed for that eye. If both eyes potentially qualify as the study eye, B-scan ultrasounds need to be taken for both eyes
- At Visit 4a (Day 28), Visit 6a (Day 63), Visit 7 (Day 77), Visit 8 (Month 3), Visit 9 (Month 9), Visit 10 (Month 15) and Visit 11 (Month 24) / the Exit Visit for the **study eye**

7.2.2. SD-OCT (6mm)

6mm SD-OCTs will be used for assessment of efficacy (total PVD, macular oedema) and safety. The images will be submitted to and evaluated by the masked CRC.

6mm SD-OCT imaging will be performed for all subjects:

- At Visit 1 (screening visit) for **potential study eye(s)**
If 1 of the subject's eyes is excluded based on an eligibility criterion that does not need confirmation by the B-scan expert reader or the CRC, no SD-OCT needs to be taken for that eye. If both eyes potentially qualify as the study eye, SD-OCT imaging needs to be performed for both eyes
- At each scheduled study visit, with the exception of Visit 2 (Day 0) and the repeat injection visits (Visit 4b [Day 35] and Visit 6b [Day 70]), for the **study eye**

7.2.3. 7-Standard Field Stereo Colour Fundus Photography

7-standard field stereo colour fundus photography will be used to assess DR stage, neovascularisation and vitreous / pre-retinal haemorrhage. The images will be submitted to and evaluated by the masked CRC.

7-standard field stereo colour fundus photographs will be taken for all subjects:

- At Visit 1 (screening visit) for **potential study eye(s)**
If 1 of the subject's eyes is excluded based on an eligibility criterion that does not need confirmation by the B-scan expert reader or the CRC, no 7-standard field stereo colour fundus photograph need to be taken for that eye. If both eyes potentially qualify as the study eye, 7-standard field stereo colour photographs need to be taken for both eyes
- At Visit 10 (Month 15) and at Visit 11 (Month 24) / the Exit Visit for the **study eye**

In addition, 7-standard field stereo colour fundus photographs will be taken for subjects that the Investigator suspects progressed to PDR:

- At Visit 8 (Month 3) and at Visit 9 (Month 9)

7.2.4. Slit Lamp Examination

Slit lamp examination will be performed for all subjects:

- At Visit 1 (screening visit), Visit 8 (Month 3), Visit 9 (Month 9), Visit 10 (Month 15) and at Visit 11 (Month 24) / the Exit Visit for **both eyes**
- At Visit 2 (Day 0), Visit 3 (Day 7), Visit 4a (Day 28), Visit 5 (Day 42), Visit 6a (Day 63) and at Visit 7 (Day 77) for the **study eye**

7.2.5. Best Corrected Visual Acuity

BCVA will be reported as the number of letters read correctly by the subject on the ETDRS chart.

BCVA will be assessed for all subjects:

- At each scheduled study visit, with the exception of the repeat injection visits (Visit 4b [Day 35] and Visit 6b [Day 70]), for **both eyes**

7.2.6. Widefield SD-OCT

Widefield SD-OCT will be used for exploratory assessment of total PVD. The images will be submitted to and evaluated by the masked CRC.

Widefield SD-OCT imaging will be performed in a subset of subjects, enrolled at sites where this is available:

- At Visit 2 (Day 0), Visit 4a (Day 28), Visit 6a (Day 63) and Visit 8 (Month 3) for the **study eye**

8. ASSESSMENT OF SAFETY

8.1. Safety Parameters

Refer to [Section 3.1.2](#) for the safety endpoints.

8.2. Methods and Timing for Assessing Safety Parameters

Refer to [Table 8](#) for an overview of which study procedures should be done by masked and the unmasked study staff and for which study procedures certification is needed.

8.2.1. Adverse Events

All AEs must be recorded from the time of providing consent until the end of the study for all subjects.

8.2.2. Full Ophthalmic Examination

A full ophthalmic examination (pupillary examination, slit lamp examination, IOP assessment and dilated fundus examination) will be performed for all subjects:

- At Visit 1 (screening visit), Visit 8 (Month 3), Visit 9 (Month 9), Visit 10 (Month 15) and at Visit 11 (Month 24) / the Exit Visit for **both eyes**
- At Visit 2 (Day 0), Visit 3 (Day 7), Visit 4a (Day 28), Visit 5 (Day 42), Visit 6a (Day 63) and at Visit 7 (Day 77) for the **study eye**

8.2.3. Best Corrected Visual Acuity

BCVA will be both a measure of efficacy and safety. Refer to [Section 7.2.5](#) for more information on the method and timing of BCVA measurement.

8.2.4. Colour Vision (Roth 28-hue)

Hue discrimination ability will be assessed by the Roth 28 Colour Test.

The Roth 28-hue colour vision test will be performed in a subset of subjects, enrolled at sites where the Roth 28 Colour Test is available, and who are ≤ 80 years of age and do not have a diagnosis of dyschromatopsia at baseline:

- At each scheduled study visit, with the exception of Visit 1 (screening) and the repeat injection visits (Visit 4b [Day 35] and Visit 6b [Day 70]), for the **study eye**

8.2.5. SD-OCT

SD-OCTs will be used both as a measure of efficacy and safety. Refer to [Section 7.2.2](#) and [Section 7.2.6](#) for more information on the timing of SD-OCT imaging.

8.2.6. Full-field ERG

ffERG readings will be submitted to and evaluated by the masked CRC.

ffERG will be performed for approximately 25% of the subjects, enrolled at sites where this is available:

- At Visit 2 (Day 0) and Visit 8 (Month 3) for **both eyes**

In addition, ffERG will be performed for subjects with expert-defined ffERG abnormalities:

- At Visit 10 (Month 15) for **both eyes** - for subjects with expert-defined ffERG abnormalities at Visit 8 (Month 3)
- At Visit 11 (Month 24) / the Exit Visit for **both eyes** - for subjects with expert-defined ffERG abnormalities at Visit 10 (Month 15)

8.2.7. Immunogenicity

An immunogenicity assay will be performed to assess whether multiple injections of ocriplasmin 0.0625mg or 0.125mg induce an immune response. Blood samples for assessment of immunogenicity will be sent to the central laboratory for immunogenicity testing.

Blood samples for immunogenicity assessment will be taken from all subjects:

- At baseline (Visit 2 [Day 0]) and at Visit 8 (Month 3)

8.3. Safety Definitions

8.3.1. Definition of an Adverse Event

An AE is any untoward medical occurrence in a patient or clinical investigation subject administered a pharmaceutical product and which does not necessarily have a causal relationship with this treatment.

An AE can therefore be any unfavourable and unintended sign (including an abnormal laboratory finding), symptom or disease temporally associated with the use of a medicinal (investigational) product, whether or not related to the medicinal (investigational) product.

8.3.2. Definition of a Serious Adverse Event

An SAE is any untoward medical occurrence that at any dose:

- Results in death
- Is life-threatening
NOTE: The term "life-threatening" refers to an event in which the patient was at risk of death at the time of the event; it does not refer to an event which hypothetically might have caused death if it were more severe
- Requires in-patient hospitalisation or prolongation of existing hospitalisation
- Results in persistent or significant disability / incapacity
- Is a congenital abnormality / birth defect

Medical and scientific judgment should be exercised in deciding whether other situations should be considered SAEs, such as important medical events that might not be immediately

life-threatening or result in death or hospitalisation but might jeopardise the patient or might require intervention to prevent one of the other outcomes listed above.

Examples of such events are intensive treatment in an emergency room or at home for allergic bronchospasm, blood dyscrasias, neoplasms or convulsions that do not result in hospitalisation.

8.3.3. Clarifications

Hospitalisation

Hospitalisation for elective treatment of a pre-existing condition (*i.e.* a condition present prior to the subject's signature of the informed consent) that did not worsen during the study is **not** considered an (S)AE. Complications that occur during hospitalisation are AEs. If a complication prolongs hospitalisation, or meets any of the other SAE criteria, the complication is an SAE.

Pre-existing Conditions, Including DR

Pre-existing conditions (*i.e.* conditions present or detected at the start of the study) which worsen during the study, exacerbation of a pre-existing illness or an increase in frequency or intensity of a pre-existing episodic event or condition are (S)AEs. Anticipated day-to-day fluctuations of pre-existing condition(s) that do not worsen with respect to baseline are **not** (S)AEs.

Worsening or progression of DR is considered to be a “lack of efficacy” or “failure of expected pharmacological action” per se and is already recorded in the efficacy data and therefore does **not** need to be reported as an (S)AE. However, the signs and symptoms and / or clinical sequelae resulting from the lack of efficacy may be reported as an (S)AE if considered by the Investigator to fulfil the definition of an (S)AE.

Medical or Surgical Procedures

Medical or surgical procedures (*e.g.* endoscopy, colonoscopy) are **not** (S)AEs; the condition that leads to the procedure is an (S)AE.

In case of elective medical or surgical procedures, or pre-study planned medical or surgical procedures for pre-existing conditions (*i.e.* a condition present prior to the subject's signature of the informed consent) that did not worsen during the study, the condition that leads to the procedure does **not** need to be reported as an (S)AE.

Death

Death is **not** an SAE; the condition that leads to death is an SAE.

Abnormal Laboratory Values

In the absence of diagnosis, abnormal laboratory values that are judged by the Investigator to be clinically significant must be recorded as an (S)AE. Clinically significant abnormal laboratory findings that are present at baseline and significantly worsen following the start of the study will also be reported as an (S)AE. However, clinically significant abnormal laboratory findings that are associated with DR, unless judged by the Investigator as more severe than expected for the subject's condition, or that are present or detected at the start of the study and do not worsen, will **not** be reported as (S)AEs.

8.4. Recording of Adverse Events

8.4.1. Adverse Events

Adverse Events (Non-serious and Serious)

(S)AEs occurring from the time of providing consent until the end of the study (Visit 11 – Month 24 / Exit Visit) must be recorded in the subject's eCRF.

(S)AEs observed during the 1-hour post-injection assessment should be recorded by the unmasked treating investigator / designee in the unmasked AE pages of the eCRF. If such an (S)AE is ongoing after the post-injection assessment, it will be followed up in a masked manner by the masked Investigator. All other (S)AEs should be recorded by the masked Investigator / designee in the masked AE pages of the eCRF.

In order to escalate relevant TEAEs in a timely manner to the DMC (refer to [Section 3.4](#)), all (S)AEs need to be recorded in the eCRF **within 24 hours** after receipt or awareness of the information.

The (S)AE term should be reported in standard medical terminology when possible. For each (S)AE, the Investigator will assess and record the date of onset, date of resolution, intensity, causality, action taken, seriousness, outcome (if applicable), and whether or not it led to withdrawal from the study.

When possible, signs and symptoms indicating a common underlying pathology should be documented as one comprehensive event with an overall diagnosis. If a diagnosis cannot be made initially, the main signs and symptoms should be documented and updated with a diagnosis when available.

Serious Adverse Events

The unmasked treating investigator / masked Investigator shall report SAEs **immediately**, and no later than 24 hours after receipt or awareness of the information, **by completing the SAE Form in the subject's eCRF**. The SAE Form should be completed as thoroughly as possible and verified with the corresponding source documents. It is very important that the Investigator provides an assessment of the relationship to the study drug or the injection procedure at the time of the initial SAE report. The eCRF system will automatically send the information to the Sponsor for processing.

If the eCRF system cannot be used for any reason, the Investigator shall submit the completed SAE Form by email or fax to the Sponsor (email: [contact]; fax: [name]), within the same timeframe. The data should be entered in the eCRF as soon as the system becomes available again.

8.4.1.1. Relationship to Study Drug or the Injection Procedure

For each (S)AE, the unmasked treating investigator / masked Investigator must determine whether the event is related to the study drug or the injection procedure. To do so, the Investigator shall determine whether, in his / her medical judgment, there is a reasonable possibility that the event may have been caused by the study drug or the injection procedure, as defined below.

Related

- There is reasonable probability that the (S)AE may have been caused by the study drug or the injection procedure; the (S)AE follows a reasonable temporal sequence from study treatment and the (S)AE cannot be reasonably explained by the subject's clinical status or other factors (*e.g.* disease under study, concurrent disease[s], and concomitant medications)

Unrelated

- There is no reasonable probability that the (S)AE has been caused by the study drug or the injection procedure; the (S)AE does not follow a reasonable sequence from study treatment, or can be reasonably explained by the subject's clinical status or other factors (*e.g.* disease under study, concurrent disease[s], and concomitant medications)

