8.6. Reporting Requirements for Serious Adverse Events

In accordance with ICH GCP, the Sponsor is responsible for the ongoing safety evaluation of an investigational medicinal product under clinical investigation. As such, the Sponsor is responsible for prompt notification to all concerned Investigators, IECs / IRBs and Regulatory Authorities of findings that could adversely affect the health of the subjects, impact the conduct of the study or alter the authorisation to continue the study.

The Sponsor or delegated Pharmacovigilance Service Provider will submit Suspected Unexpected Serious Adverse Reactions (SUSARs) to the Regulatory Authorities in an expedited manner as follows:

- Fatal or life-threatening SUSARs – as soon as possible but no later than 7 calendar days after the Sponsor's first knowledge of the minimum criteria for expedited reporting

- Non-fatal and non-life-threatening SUSARs – as soon as possible but no later than 15 calendar days after the Sponsor’s first knowledge of the minimum criteria for expedited reporting
- Relevant follow-up information for fatal or life-threatening SUSARs – within an additional 8 calendar days

Where required by IEC / IRB procedure, it is the Principal Investigator’s responsibility to notify the IEC / IRB of all SUSARs / SAEs that occur at his / her site.

SUSARs that have arisen in other clinical studies of the same sponsor and with the same study drug and that could have consequences for the safety of the subjects involved in the clinical study that was assessed by the concerned IEC / IRB will be reported in accordance with the requirements of the concerned IEC / IRB.

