3. Conventions for Analysis and Computations

All Treated Subjects Analysis Set

A single analysis set will be used. The All Treated Subjects analysis set will include subjects who are randomized and receive the first injection of study treatment. Subjects will be assigned to the treatment they receive at the time of the first injection.

Baseline Value

Baseline value is defined as the last non-missing value prior to administration of the first injection of the study drug.

Change from Baseline

Change from Baseline is calculated as the difference between the value at a considered visit minus the Baseline value. Change from Baseline will be missing if either one of the Baseline Value or the value at the considered visit is missing.

Adverse Events

Adverse events are coded using MedDRA version 18.1.

If a subject has multiple occurrences of an AE after an injection, the subject is presented only once in the respective subject count. Events are counted each time in the event column. Ocular adverse events are those that occur in either eye. Events recorded as OU (both eyes) are counted once for the study eye and once for the non-study eye, and are counted as 2 separate ocular events.

Drug related events are events considered by the Investigator with a reasonable possibility that the study treatment caused the event or events with a missing relationship.

Where severity is missing, the adverse event will be assigned to the ‘severe’ category.

AEs will be attributed to the closest injection prior to the occurrence of the event. AEs with a start date corresponding to the date of one of the injections will be attributed to that particular injection.

Treatment Emergent Adverse Events

Treatment Emergent Adverse Events are adverse events with a start date on or post the date of the first injection, or a missing start date.

Concomittant Interventions/Anti-VEGFs

Concomittant Interventions (including Anti-VEGFs) are interventions with a start date on or post the date of the first injection, or a missing start date.

Imputation of Partially Missing Dates

The conventions for imputing partially missing dates are provided in the appendix of this document.

Age Computation

The Date of Birth (DOB) will be imputed to 01JULYYYY where YYYY correspond to the year of birth. The following SAS code will be used for calculating age.

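### The protocol's definition of a related adverse event contradicts the reasonable-possibility test that introduces it and that the SAP reports, so drug-related events are likely to be under-counted

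*Protocol*

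**What the plan says.** Protocol section 8.4.1.1 opens by asking the investigator to use medical judgement on whether "there is a reasonable possibility that the event may have been caused by the study drug or the injection procedure, as defined below".

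The definition of Related that follows has three elements:

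- It begins: "There is reasonable probability that the (S)AE may have been caused by the study drug or the injection procedure".
- It requires a reasonable temporal sequence from treatment.
- It requires that "the (S)AE cannot be reasonably explained by the subject's clinical status or other factors". The examples of such factors are "disease under study, concurrent disease[s], and concomitant medications".

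The definition of Unrelated begins with the absence of a reasonable probability of causation. It then says that the event lacks a reasonable sequence from treatment, "or can be reasonably explained by the subject's clinical status or other factors".

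SAP section 3, under Adverse Events, says: "Drug related events are events considered by the Investigator with a reasonable possibility that the study treatment caused the event". It adds events whose relationship is missing.

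Two uses of the classification follow. Protocol section 9.6.2 plans a summary of study drug-related AEs and a tabulation by relationship. Protocol section 8.6 says that the sponsor or its pharmacovigilance provider "will submit Suspected Unexpected Serious Adverse Reactions (SUSARs) to the Regulatory Authorities in an expedited manner".

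**The concern.** The factor that must be excluded before an event can be Related is, first of all, diabetic retinopathy, and every subject in the trial has it. The definition therefore works against Related for exactly those ocular events that are hardest to attribute and that matter most for an intravitreal enzyme.

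Protocol section 8.3.3 already exempts worsening of diabetic retinopathy itself from AE reporting and leaves its signs and sequelae to the investigator's judgement. The causality definition is thus a second filter on events that resemble the disease.

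At stake is what the drug-related AE tables mean. A reader of the report would take them as events with a reasonable possibility of a drug cause, as the SAP labels them. An investigator who followed the definition would have recorded something narrower.

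**Working it through.** No sample size, power or event count bears on this point, so the check is a comparison of the rules.

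**Step 1: the rules as yes/no conditions.** Let A = a reasonable causal possibility, T = a reasonable temporal sequence, E = reasonably explained by the disease or another factor. Possibility and probability are treated as the same thing here, which favours the plan. Any real difference between them widens the gap.

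- Lead-in, and the SAP label: Related if A.
- Definition of Related: A and T and not E.
- Definition of Unrelated, reading 1 (the second half of the sentence defines the category): not T, or E.
- Definition of Unrelated, reading 2 (every element must hold): not A, and (not T, or E).

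| A | T | E | Lead-in / SAP | Definitions, reading 1 | Definitions, reading 2 |
|---|---|---|---|---|---|
| yes | yes | no | Related | Related | Related |
| yes | yes | yes | Related | Unrelated | neither |
| yes | no | no | Related | Unrelated | neither |
| yes | no | yes | Related | Unrelated | neither |
| no | yes | no | not related | neither | neither |
| no | yes | yes | not related | Unrelated | Unrelated |
| no | no | no | not related | Unrelated | Unrelated |
| no | no | yes | not related | Unrelated | Unrelated |

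The lead-in gives Related in 4 of 8 rows and the definition in 1 of 8. Rows 3 and 4 will seldom arise, because a causal possibility without suitable timing is rare. Row 2 is the one that matters: plausible cause, right timing, and also explainable by the disease. It is Related under the lead-in and can never be Related under the definition, whichever way Unrelated is read.

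**Step 2: does row 2 occur in this trial?** Retinal haemorrhage is a direct example.

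- Protocol section 1.1.1 names intraretinal haemorrhages among the features of the non-proliferative stages, which is the stage enrolled. So E can be yes.
- Protocol section 1.3.2 reports on 62 subjects with diabetic retinopathy given ocriplasmin 0.125mg. Of these, 37 (37/62 = 59.7%) had ocular TEAEs in the study eye, and retinal haemorrhage was among the most frequent. So A can be yes.
- Protocol section 1.5.1.2 puts intraocular haemorrhage at 1.3% per intravitreal injection, and causality to the procedure must be judged as well.

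No separate count of retinal haemorrhage is given, so the number of events in row 2 cannot be calculated.

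**Step 3: direction by arm.** The same rule applies in every arm. By protocol section 3.6.1, however, a sham injection does not penetrate the globe. True drug or injection effects, and so the related events that can be lost, lie chiefly in the ocriplasmin arms.

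**Step 4: which outputs depend on relatedness?**

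- Dependent: the drug-related AE summary and the tabulation by relationship (protocol 9.6.2, SAP section 3), and the causality part of identifying suspected reactions (protocol 8.6).
- Not dependent: ocular TEAEs in the study eye (protocol 3.1.2 and 9.6.1), loss of 15 or more letters (9.6.1), the SAE summaries (9.6.2), and the escalation list for the DMC (3.4).

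**The case against.** The best case against the point is that its practical reach is small. The main safety outputs do not use investigator attribution, the sham arm offers a comparison free of it, and no safety testing is planned. The SAP counts a missing relationship as related and rests on what the investigator considered, which echoes the protocol's lead-in. The SAP is an abbreviated version, and the eCRF field and site manuals are not available, so investigators may in practice have used the broader test. All of this stands, and it limits the consequence. It does not reconcile the two tests.

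Four stronger readings are tempting, and the documents do not support them.

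- *The text forces such events into Unrelated.* It does so only on reading 1. Unrelated opens by requiring no reasonable probability of causation, so on reading 2 the event fits neither category.
- *Treatment-related events will drop out of expedited reporting.* This is possible but not shown. All SAEs reach the sponsor within 24 hours whatever their causality (protocol 8.4.1). A sponsor causality assessment is neither described nor excluded. An event must also be unexpected to be a SUSAR, and that cannot be settled without the reference safety documents.
- *Retinal tears, detachment and severe vision loss can nearly always be put down to the disease.* Protocol section 1.1.1 ties these to the proliferative stage. The trial enrols non-proliferative eyes and excludes tears, rhegmatogenous detachment and vitreous haemorrhage at entry (4.1.1.2). The argument would apply mainly after progression.
- *The SAE counts in protocol section 1.5.1.1 measure the problem.* Retinal detachment and reduced visual acuity give 26 + 16 = 42 of 435 SAEs, or 9.7%. That total pools 336 SAEs on ocriplasmin with 99 on sham or placebo, in an earlier programme for another indication. It is not an estimate of misclassification here.

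**Conclusion.** The protocol contradicts itself on causality, and the SAP puts the broader label on data collected under a section whose operative definition is narrower. Where investigators followed the definition, events with both a plausible treatment cause and a plausible disease cause are missing from the drug-related count. The bias is downward and falls chiefly on the ocriplasmin arms.

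Its size is unknown and cannot be derived from the documents. It depends on how many events have both explanations, and on which of the two tests investigators actually applied. The harm is confined to the descriptive drug-related AE summaries and, possibly but not certainly, to the set of events considered for SUSAR reporting. The trial's principal safety results stand as planned. Correction is warranted because the remedy is almost free and the drug-related table cannot be interpreted without it.

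**What to change.** Use one standard in protocol section 8.4.1.1 and match it in SAP section 3:

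- **Related:** a reasonable possibility that the study drug or the injection procedure caused or contributed to the event, even if another cause is possible.
- **Unrelated:** no reasonable possibility.

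Delete the condition that the event cannot be reasonably explained by other factors, and record any alternative cause in its own eCRF field. Two small alignments belong with this. Section 8.4.1.4 uses a third wording (possibly related) for SAEs learned of after a subject has completed the study. The SAP definition names the study treatment but not the injection procedure. The protocol should also say who decides causality for SUSAR purposes.

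The final analysis followed the Month 24 visit, so data already collected cannot be re-judged by rewording. For these data, the report should state which definition investigators applied and show ocular TEAEs irrespective of relatedness beside the drug-related table.

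The cost is protocol and SAP wording, the eCRF completion guideline and a note to sites for future use, and one table placement and a sentence in the report. The downside is small: somewhat more events will be coded as related and reviewed.
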